4.13.2. Physical Examination and Growth Parameters

Physical examination (general appearance; skin; head, ears, eyes, nose, and throat [HEENT]; etc.) results will be summarized in a shift table from Baseline, and abnormal results will also be summarized.

Growth Parameters (height, weight, body mass index [BMI]) will be summarized by age-normative z-scores. The age-normative height, weight, and BMI scores will be based on a Centers for Disease Control and Prevention (CDC) SAS macro which calculates the percentiles and z-scores for a child's sex and age.

The CDC SAS macro is found here (date accessed: 08Sep2019):

<https://www.cdc.gov/nccdphp/dnpao/growthcharts/resources/sas.htm>

These summaries will be performed on the Safety Population.

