### *Safety Monitoring*

The safety measures used in this study are standard and reflect appropriate monitoring of pediatric patients receiving an investigational drug. Although no adrenal abnormalities have been observed in the Phase 1/2 study, CAT-1004-201 (see the Investigator's Brochure), since weight loss and adverse effects on adrenal glands were observed in 13-week juvenile rat toxicology studies at plasma exposures higher than anticipated in humans, monitoring of adrenal function will be included in this study as a precaution. In addition to monitoring by the Investigators, sub-Investigators and Medical Monitors, a DSMB will provide oversight of the study.

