### **9.12.1. Physical Examination, Growth Parameters, Electrocardiograms, and Vital Signs**

Physical examination (general appearance, skin, HEENT, etc.) abnormal results will be summarized. Physical examination results will also be summarized in a shift table from Baseline.

Growth parameters (height, weight, BMI) will be compared to age-normative percentiles.

ECG results will be summarized at each timepoint, and also using shift tables from Baseline.

Vital signs (temperature, heart rate, respiratory rate, and systolic and diastolic blood pressure), and changes from Baseline in vital signs, will be summarized descriptively at Baseline and other study timepoints. Data listings will be provided.

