4.13. Safety Analyses

Safety analyses will be conducted using the Safety Population. Results of all safety assessments will be listed by patient, and summarized by treatment group and time point as applicable. These safety analyses will be compared qualitatively between treatment groups; however, there will be

no inferential statistical comparisons between groups (except for specific analyses, noted below).

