4.13.3. Laboratory Data

Values at all study time points and changes from Baseline to post-Baseline time points in clinical chemistry, hematology and urinalysis results will be summarized descriptively.

Abnormal clinical laboratory values will be identified as outside (above or below) the normal range and will be evaluated for clinically notable abnormalities.

All laboratory data and normal ranges will be provided in data listings. A subset listing will be presented for all abnormal laboratory values (i.e., values which are indicated as being notable or critical low/high).

The following abbreviations for flags in the central lab database.

- L: Reference Low
- NL: Notable Low
- CL: Critical Low
- R: Rechecked Value
- H: Reference High
- NH: Notable High
- CH: Critical High

In addition, to assess decreases in creatine kinase (CK), the change from baseline in CK will be assessed at each scheduled assessment visit using a non-parametric signed rank test (for a within-group comparison) and a Wilcoxon rank sum test for the comparison of edasalonexent versus placebo.

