4.13.4. Vital Signs

The actual value and change from Baseline will be summarized for vital signs (temperature, heart rate, respiratory rate, and systolic and diastolic blood pressure) descriptively at Baseline and other study time points.

By-patient listings of vital sign measurements will also be provided.

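### SAP 4.13.2 specifies no change from Baseline in height, weight or BMI z-score, unlike laboratory values, vital signs and ECG, so small growth shifts would be estimated imprecisely

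*SAP*

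**What the plan says.** SAP 4.13.2 covers growth in one sentence: "Growth Parameters (height, weight, body mass index [BMI]) will be summarized by age-normative z-scores". It adds that a CDC macro supplies the percentiles and z-scores and that the Safety Population is used. Protocol 9.12.1 is equally short: "Growth parameters (height, weight, BMI) will be compared to age-normative percentiles". Neither names a change from Baseline.

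The neighbouring safety domains do:

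- Physical examination, in the same SAP section: "results will be summarized in a shift table from Baseline, and abnormal results will also be summarized".
- Laboratory data, SAP 4.13.3: "changes from Baseline to post-Baseline time points in clinical chemistry, hematology and urinalysis results will be summarized descriptively".
- Vital signs, SAP 4.13.4: "The actual value and change from Baseline will be summarized for vital signs". The list that follows does not include height or weight.
- ECG, SAP 4.13.5: a Week 52 change-from-Baseline ANCOVA with treatment and the Baseline value in the model.

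A general rule in SAP 4.13 also applies to growth: "Results of all safety assessments will be listed by patient, and summarized by treatment group and time point as applicable". The same section rules out inferential between-arm safety comparisons, apart from specific analyses that the SAP goes on to name.

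**The concern.** Safety is a secondary objective, and SAP 2.6.4 names height and weight as safety parameters. The disease background in Protocol section 2 lists growth inhibition and weight gain among the harms that limit steroid use. Section 2 and section 3.4 present edasalonexent as working through a shared pathway without those side effects. A reader of the study report will therefore want to know whether treated boys grew differently from boys on placebo, and how precisely that is known.

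A boy's height or weight z-score at Week 52 depends largely on where he started. A table of levels by arm carries all of that between-boy spread, plus any chance Baseline imbalance. The information that removes most of it, each boy's own Baseline, is already collected. If within-boy change is not specified, the report may lack a usable estimate of a small effect on growth. It would then give weak support either for a growth effect or for its absence.

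**Working it through.** **Is there a planned figure to reproduce?** No. The documents give no SD, correlation, target difference or power for growth. The sample size section supplies only the number of boys.

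**Inputs from the documents (SAP 4.1).** 126 boys randomised 2:1 is 84 vs 42. With about 20% dropout this becomes 84 × 0.8 = 67.2 and 42 × 0.8 = 33.6, about 67 vs 34 at Week 52.

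**Assumptions (not in the documents).** Z-score SD 1.0, with 0.8 to 1.2 as a range. Within-boy correlation r between Baseline and Week 52 from 0.5 to 0.95.

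**What the planned table can yield.** If the same boys contribute at both visits, mean change equals the difference of the two visit means. Its spread does not follow from that table: SD(change) = sqrt(s0² + s1² − 2·r·s0·s1), and r is not shown. With both SDs equal to 1 this is sqrt(2(1 − r)), which is 1.00 at r = 0.5 and 0.32 at r = 0.95. The same pair of columns therefore fits a threefold range of precision. The subtraction itself is exact only if the same boys are present. About 20% dropout is assumed, and under Protocol Appendix 2 a cancelled Week 52 site visit takes weight on a home scale and height only where it can be obtained.

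**Precision of the between-arm difference at Week 52 (67 vs 34, SD 1.0).**

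- Levels: SE = sqrt(1/67.2 + 1/33.6) = 0.211; 95% half-width = 1.96 × 0.211 = 0.41 z. Over SD 0.8 to 1.2 it is 0.33 to 0.50 z.
- Change: SE = 0.211 × sqrt(2(1 − r)).
- Baseline-adjusted: SE = 0.211 × sqrt(1 − r²), a large-sample approximation.

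| r | Half-width, levels | Half-width, change | Half-width, Baseline-adjusted | SE ratio, levels to change |
|---|---|---|---|---|
| 0.5 | 0.41 | 0.41 | 0.36 | 1.0 |
| 0.7 | 0.41 | 0.32 | 0.30 | 1.3 |
| 0.8 | 0.41 | 0.26 | 0.25 | 1.6 |
| 0.9 | 0.41 | 0.19 | 0.18 | 2.2 |
| 0.95 | 0.41 | 0.13 | 0.13 | 3.2 |

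Change beats levels only when 2(1 − r) is below 1, that is when r exceeds 0.5. The adjusted factor sqrt(1 − r²) never exceeds 1.

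**Which effects are affected.** As a yardstick of precision only, since no growth test is planned, this is the chance that a 95% CI excludes zero with 67 vs 34 boys and SD 1.0:

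| True difference | Levels | Change, r = 0.8 | Change, r = 0.9 | Change, r = 0.95 |
|---|---|---|---|---|
| 0.2 z | 16% | 32% | 56% | 85% |
| 0.3 z | 29% | 61% | 89% | 99% |
| 0.5 z | 66% | 96% | over 99% | over 99% |

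With all 84 vs 42 boys, levels alone reach 75% for 0.5 z.

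**The case against.** The best reply is that the SAP is silent on change and does not exclude it. Summaries by arm and visit would show Baseline, any imbalance and the drift. Mean change can be approximated by subtraction, and the listings let anyone compute each boy's change. The table shells are in a separate document that may already have such columns. This stands as far as it goes: the data are not lost. But subtraction gives no SD or interval for change and is inexact when boys drop out. Listings are not an analysis, and unseen shells cannot be credited with filling a gap in the SAP text.

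A second reply is that growth is compared only qualitatively, so power is beside the point. That is fair, and the figures above should be read as measures of precision. A descriptive comparison still benefits from a narrower interval.

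A third reply is that parity with laboratory values and vital signs needs only a change column, and that an adjusted between-arm contrast goes further. That is true. ECG parameters and creatine kinase are written exceptions, not general permission, so the contrast has to be added as an exception in its own right.

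Two stronger readings are tempting. A reader might infer that the protocol links growth analysis to the juvenile rat findings, because section 3.4 reads "since weight loss and adverse effects on adrenal glands were observed in 13-week juvenile rat toxicology studies". The sentence goes on to place those findings at exposures above those expected in patients and concludes "monitoring of adrenal function will be included in this study as a precaution"; it does not mention growth analysis. The steroid comparison is the better-documented reason. A reader might also infer that between-boy spread hides any one-year effect. On the assumptions above, a 0.5 z difference has a 66% to 75% chance of showing even on levels.

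**Conclusion.** The gap is real and modest. No change from Baseline is specified for height, weight or BMI in either document, although adjacent safety domains have it and the Baseline values are collected. The consequence is imprecision for small shifts, about 0.2 to 0.3 z; larger effects would not be concealed. Assuming SD 1 and 67 vs 34 boys, the 95% half-width is about 0.41 z on levels and 0.26 to 0.13 z on change for correlations of 0.8 to 0.95.

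That gain rests entirely on the assumed correlation and falls to nothing for change alone at 0.5. A flat statement that change is twice as precise would hold only near 0.9. SD 1 is the reference-population value, and the documents give none for these boys. No efficacy conclusion depends on this point.

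**What to change.** In SAP 4.13.2:

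- Add a descriptive summary of change from Baseline in height, weight and BMI z-score, by arm, at each visit where measured. By Protocol Appendix 1 that is Weeks 13, 26, 39 and 52 for weight, and Weeks 26 and 52 for height and hence BMI.
- At Week 52 add the between-arm difference in z-score, adjusted for the Baseline z-score, with a 95% CI. Label it descriptive, give no p-value, and list it among the specific exceptions that SAP 4.13 allows. The ECG model in SAP 4.13.5 is a ready template.
- Keep the z-score levels by arm and visit, and show the number of boys contributing to each change.

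The cost is a few lines of SAP text and some extra table columns, with no new measurements. The small downside is one more between-arm safety estimate for readers to interpret.

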4.13.3. Laboratory Data

Values at all study time points and changes from Baseline to post-Baseline time points in clinical chemistry, hematology and urinalysis results will be summarized descriptively.

Abnormal clinical laboratory values will be identified as outside (above or below) the normal range and will be evaluated for clinically notable abnormalities.

All laboratory data and normal ranges will be provided in data listings. A subset listing will be presented for all abnormal laboratory values (i.e., values which are indicated as being notable or critical low/high).

The following abbreviations for flags in the central lab database.

- L: Reference Low
- NL: Notable Low
- CL: Critical Low
- R: Rechecked Value
- H: Reference High
- NH: Notable High
- CH: Critical High

In addition, to assess decreases in creatine kinase (CK), the change from baseline in CK will be assessed at each scheduled assessment visit using a non-parametric signed rank test (for a within-group comparison) and a Wilcoxon rank sum test for the comparison of edasalonexent versus placebo.

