consistent with positive edasalonexent treatment effects. Four muscle enzymes (creatine kinase, alanine aminotransferase, aspartate aminotransferase and lactate dehydrogenase) were significantly lower compared to Baseline following 12 weeks of edasalonexent treatment and at later time points, consistent with a slowing of muscle degeneration and an improvement in muscle integrity. A composite of magnetic resonance imaging (MRI) T2 rates of change in five lower leg muscles was also significantly improved through 48 weeks of 100 mg/kg/day edasalonexent treatment compared to the off-treatment control period, consistent with a reduction of inflammation in the muscle. Improvements were also seen in rates of change in both soleus and vastus lateralis magnetic resonance spectroscopy (MRS) fat fraction through 48 weeks of edasalonexent treatment compared to the off-treatment control period, consistent with a reduction of fat in the muscle. Edasalonexent remained well tolerated and no safety signals were observed. The most common adverse events, gastrointestinal, were typically mild and transient. Based on emerging safety and efficacy data, all patients moved to 133 mg/kg/day (33/33/67 mg/kg in 3 divided doses) in the open-label extension.

As of June 2018, 32 pediatric patients had received up to 112 weeks of active dosing with edasalonexent at doses up to 133 mg/kg/day, with a total combined exposure of over 45 years, with no safety concerns. More detailed information on clinical studies and potential clinical risks of edasalonexent can be found in the Investigator's Brochure.

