### 5.2.5. Treatment Discontinuation

A patient's study treatment may be discontinued at any time at the patient's/parent/legal guardian's request or at the discretion of the Investigator, Medical Monitor or Sponsor. The following may be justifiable reasons for the Investigator, Medical Monitor or Sponsor to discontinue a patient from treatment:

- The patient experiences an intolerable or unacceptable AE
- The patient is unable to comply with the requirements of the protocol
- The patient participates in another investigational study without the written authorization of the Sponsor

Discontinuation of treatment does not imply withdrawal from the study.

Patients who discontinue treatment prematurely will be asked to complete the early termination visit prior to their last dose of study drug as noted in the SOA in [Appendix 1](#).

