**APPENDIX 1. SCHEDULE OF ASSESSMENTS**

Study Week(s)	Screen a	BL b	Double Blind, Placebo-Controlled Treatment (Weeks 1 - 52)								Safety F/U c
	-4 - 0	0	6	13	19	26	32	39	45	52/ET d	
Informed Consent/Assent	X										
Site Visit e	X	X		X		X		X		X	
Site Call e, f			X		X		X		X		X
Med History/Demographics	X										
Confirm Eligibility	X	X									
Randomization g		X									
Vital Signs	X	X		X		X		X		X	
Weight	X	X		X		X		X		X	
Height		X				X				X	
Physical Examination	X	X		X		X		X		X	
AEs/Con Meds h	X		Continuous								
12-Lead ECG i	X					X				X	
Cardiac Monitoring j	X					X				X	
Hematology/Chemistry k	X	X		X		X		X		X	
ACTH/Cortisol k		X		X		X		X		X	
Urinalysis	X					X				X	
DNA Sample l		X									
Biomarkers, Gene Expression k		X		X		X		X		X	
NSAA, Stand from Supine, 10MWT, 4-Stair Climb, Muscle Strength m	X	X		X		X		X		X	
PUL n		X				X				X	
Videotape Functional Assessments o	X	X								X	
PODCI p		X								X	
Lateral Spinal Radiography, DXA q		X								X	
Study Drug Questionnaire						X					
Nutritional Guidance r		X									
Drug Dispensation		X		X		X		X			
Drug Accountability				X		X		X		X	
PK (plasma and urine) s				X		X				X	

a Per Investigator's discretion, informed consent, medical history/demographic data and lab assessments may be completed remotely by a qualified medical professional.

b The first day of study drug is "Day 1"; unless otherwise specified, all assessments should be completed within a 4 week window prior to Day 1.

c Safety follow-up should occur within 2 wks. after last dose of study drug. Patients continuing in the open-label extension study are not required to perform the safety follow-up.

d If patient discontinues treatment early, patient will be asked to return for early termination (ET) visit prior to their last dose of study drug. Functional assessments performed within 6 weeks of discontinuing treatment do not need to be repeated at the ET visit. If the ET visit occurs after drug has been discontinued, certain assessments may be omitted per Sponsor discretion.

- e Weeks 6-19 should be conducted within the study week with a  $\pm 4$ -day window. Weeks 26-54 have a  $\pm 10$ -day window.

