4.2.4. Adjustments for Covariates

Statistical models will adjust for the stratification variables as covariates.

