4.10. Efficacy Evaluation

The FAP is used as the primary population, and the PP and Randomized Populations will be used for sensitivity analyses as described for each efficacy analysis below.

Efficacy endpoints will be listed by patient, and summarized by treatment group and time point, as applicable. For the timed function tests, both the times to complete (seconds) and their speed (i.e. the reciprocals) will be tabulated. In the case of the 10MWT, units will be 10 meters per second. In the case of the stand from supine and the 4-stair climb, units will be task per second. Descriptive statistics will be calculated for quantitative efficacy data as well as for the CFB, and differences between treatment groups as applicable.

Summary statistics for the primary and secondary efficacy endpoints will be presented by investigative site and overall.

If a patient initiates corticosteroid therapy or discontinues study treatment, all observations from that patient after these events will be censored from the efficacy analyses.

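### The between-arm creatine kinase (CK) test in SAP 4.13.3 is valid but inefficient: it ignores the baseline CK already collected and yields no effect estimate (minor)

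*SAP*

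**What the plan says.** SAP 4.13.3 summarises laboratory data descriptively but singles out CK for testing, with the stated aim of assessing decreases. Within each arm, "the change from baseline in CK will be assessed at each scheduled assessment visit using a non-parametric signed rank test"; between arms it specifies "a Wilcoxon rank sum test for the comparison of edasalonexent versus placebo". It names no transformation, baseline covariate, stratification factor, between-arm estimate or confidence interval.

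Related text:

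- **Population.** SAP 4.13: "Safety analyses will be conducted using the Safety Population". By SAP 3.1 that set includes the non-randomised second siblings, and it has no counterpart to the eteplirsen exclusion in the Full Analysis Population (FAP).
- **Censoring.** After corticosteroid start or treatment discontinuation, SAP 4.10 says "all observations from that patient after these events will be censored from the efficacy analyses". SAP 4.13 has no equivalent rule.
- **Neighbouring safety tests.** SAP 4.13.5 gives ECG parameters an ANCOVA with the baseline value, and heart rate a repeated-measures model with baseline heart rate.
- **Background.** Protocol 2.2 reports that four muscle enzymes, CK among them, "were significantly lower compared to Baseline following 12 weeks of edasalonexent treatment".
- **Data available.** CK is part of clinical chemistry (Protocol Appendix 3), scheduled at Screening, Baseline and Weeks 13, 26, 39 and 52 (Protocol Appendix 1).
- **Status.** SAP 4.2.1 limits formal testing to the primary and secondary endpoints, and CK is not in the SAP 4.2.5 hierarchy.

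**The concern.** Asking whether CK falls on drug is a drug-effect question. The earlier evidence in Protocol 2.2 compares CK with Baseline, so this trial is an opportunity for a concurrent placebo comparison. The planned test uses baseline CK only by subtracting it. When baseline and follow-up are imperfectly correlated, subtraction removes less noise than regression on baseline. If CK is roughly log-normal, ranking absolute changes adds further noise, because a given proportional fall is a large absolute fall in a boy who starts high.

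At stake is the sensitivity and usefulness of an exploratory result. A real reduction could go undetected, and the planned output is a p-value beside descriptive changes, with no estimate of the size of the effect. A secondary question is whether the population and follow-up suit a drug-effect aim.

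**Working it through.** **Plan's own figure.** There is none for CK. The approximately 80% power in SAP 4.1 concerns NSAA. With 126 × 0.8 = 100.8 evaluable at 2:1, 0.625 × √(67.2 × 33.6 / 100.8) = 2.958, and Φ(2.958 − 1.960) = 0.84. The stated figure is slightly conservative, and the CK point does not depend on it.

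**Inputs.** From the documents: 126 boys at 2:1 and about 20% dropout, giving roughly 67 versus 34 at a late visit. A lighter loss of about 10% (126 × 0.9 = 113.4) gives 76 versus 38. Assumed, because the documents give no CK distribution: log-normal CK, true ratio 0.80, log SD 0.4 or 0.6, baseline to follow-up correlation r from 0.3 to 0.85.

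**Why baseline adjustment helps.** On the log scale a change score has variance 2σ²(1 − r). After regression on baseline the variance is σ²(1 − r²). The ratio is (1 + r)/2, so an unadjusted change needs 2/(1 + r) times as many boys: 1.54 at r = 0.3, 1.33 at 0.5, 1.18 at 0.7.

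**Hand check of ANCOVA power** (76 versus 38, σ = 0.4, r = 0.3). Effect: ln 0.80 = −0.223. Standard error: 0.4 × √0.91 × √(1/76 + 1/38) = 0.0758. Power: Φ(0.2231/0.0758 − 1.960) = Φ(0.98) = 0.84. The simulation below gives 82%.

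**Simulation.** 10,000 trials per cell at a single visit, bivariate normal log CK, two-sided 0.05; Monte Carlo standard error at most 0.5 point. Entries are power in %, Wilcoxon on raw change → ANCOVA of log CK on log baseline CK.

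| Log SD | r | 76 vs 38 | 67 vs 34 |
|---|---|---|---|
| 0.4 | 0.3 | 56.0 → 82.1 | 51.7 → 78.5 |
| 0.4 | 0.5 | 69.4 → 89.2 | 64.6 → 85.1 |
| 0.4 | 0.7 | 88.9 → 97.4 | 84.9 → 95.4 |
| 0.4 | 0.85 | 99.3 → 100.0 | 98.5 → 99.9 |
| 0.6 | 0.3 | 29.2 → 48.9 | 26.2 → 45.1 |
| 0.6 | 0.5 | 36.9 → 55.8 | 33.6 → 51.5 |
| 0.6 | 0.7 | 54.9 → 73.3 | 50.7 → 69.0 |
| 0.6 | 0.85 | 82.9 → 94.0 | 79.2 → 91.3 |

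For r = 0.3 to 0.7 the smallest gap is 97.4 − 88.9 = 8.5 points and the largest 78.5 − 51.7 = 26.8. Smaller simulations of the same model spread this to about 8 to 29, which is simulation error. At r = 0.85 the gap is about 1 point at log SD 0.4 and 11 to 12 at log SD 0.6. Null rejection was 4.7% to 5.1% for every method.

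**Source of the loss.** At log SD 0.4, r = 0.3, 76 versus 38, Wilcoxon on log change has about 63% power. Taking logs therefore recovers about 7 points, and most of the loss comes from not adjusting for baseline.

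**Heavy tails.** Log CK with t-distributed errors (3 df), 76 versus 38; power in % for Wilcoxon / log-ANCOVA / rank ANCOVA with baseline:

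- Log SD 0.4: 89.0 / 90.7 / 95.4 at r = 0.5; 98.1 / 96.7 / 98.7 at r = 0.7.
- Log SD 0.6: 57.4 / 61.9 / 69.1 at r = 0.5; 77.6 / 76.5 / 80.3 at r = 0.7.

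Log-ANCOVA roughly ties at 0.5 and falls slightly behind at 0.7; rank ANCOVA stays ahead. At r = 0.85 rank ANCOVA is level with the Wilcoxon or about 1 point below.

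**Off-drug values (illustration only).** With 84 versus 42, ratio 0.75, log SD 0.5, r = 0.5, suppose a share of the active arm has lost the drug effect. Wilcoxon power is 75%, 71%, 65% and 54% at shares of 0, 5, 10 and 20%. The documents give no such share.

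**The case against.** The strongest reply is that nothing is broken. A distribution-free test is a standard choice for a laboratory value, its error rate is correct, and nothing confirmatory depends on it. That stands, and it limits this to a minor point. It is also fair that the main table shows log-ANCOVA under its ideal model, and that the simulation is a single-visit ANCOVA on equal numbers, whereas the fix is a repeated-measures model on a somewhat smaller set. Rank ANCOVA answers the distributional part, since its advantage does not rest on log-normality.

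Several stronger readings are tempting but lack support:

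- **That off-drug and post-steroid CK values are kept and blur the effect.** Such values can arise: "Discontinuation of treatment does not imply withdrawal from the study", and Protocol Appendix 1 foresees late early-termination visits ("If the ET visit occurs after drug has been discontinued, certain assessments may be omitted per Sponsor discretion"). But keeping them is inferred from the absence of a rule. They may be few, since the early-termination visit is requested before the last dose and corticosteroids are prohibited during the study. The documents do not say which way steroids move CK.
- **That the CK population wrongly differs from the NSAA population.** The SAP never says CK is meant to support NSAA.
- **That SAP 4.2.4 is breached.** It reads "Statistical models will adjust for the stratification variables as covariates", and a rank sum test is not a statistical model in that sense.
- **That a chance baseline imbalance passes straight into the result.** A change score subtracts baseline. On the log scale what remains is −(1 − r) times the imbalance, so half of it, reversed in sign, at r = 0.5.
- **That CK is the only drug-response measure tested between arms.** Heart rate is too, and Protocol 6.7 reports an earlier fall in heart rate.

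**Conclusion.** The point holds as a minor inefficiency. The CK comparison leaves out a baseline covariate that is already collected, without a stated reason and unlike the ECG and heart-rate analyses beside it, and no between-arm estimate is requested. Under the log-normal assumptions above, the planned test gives up about 9 to 27 points of power at correlations of 0.3 to 0.7. The loss is small at a correlation of 0.85 with log SD 0.4. Under heavy tails the case rests on rank ANCOVA more than on log-ANCOVA.

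These sizes depend on an assumed CK variance, correlation, skew and effect, none of which the documents supply. A reader might infer that the planned test is invalid or that it threatens the trial's conclusions; neither is so. The population and censoring question is secondary and its size cannot be determined from the documents.

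**What to change.** In SAP 4.13.3, before unblinding:

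1. Add the SAP 4.10.1 repeated-measures model with log CK as the outcome, replacing baseline NSAA and its visit interaction with log baseline CK and its visit interaction, and keeping the other covariates. Report the edasalonexent/placebo geometric mean ratio with 95% confidence interval at each visit.
2. Add rank ANCOVA on baseline CK at each visit as a robustness check.
3. Because the aim is a drug effect, run the added model on the FAP with the SAP 4.10 censoring rule, and state explicitly how off-drug and post-steroid CK values are handled in each analysis.
4. Keep the Wilcoxon test on the Safety Population as supportive, and label all CK testing exploratory.

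Cost: a paragraph of SAP text, one model and one simple check, with no new data. The downsides are an approximate log-normality assumption, which items 2 and 4 guard against, and a somewhat smaller analysis set.
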